11.1 Sample Size

The sample size of 50-60 patients is determined per Chinese regulatory requirements and agreement for a regional study of a medical device already approved in other regions based on a well-designed prospective study.

11.2 Timing

Study subjects will undergo screening and pre-procedure visits, and then follow-up visits at Discharge, and 30 Days (+14 days) for Endpoint analysis. Long-term follow-up data is collected at 6 Months (+/- 30 days), 1 Year (+/- 60 days), 2 Years (+/- 60 days), 3 Years (+/- 60 days), 4 Years (+/- 60 days), and 5 Years (+/- 60 days).

11.3 Analysis Sets

- As Treated (AT) Population: all patients that were enrolled in the trial for whom the SAPIEN XT valve implant procedure was begun, defined as the time in which the first Edwards' investigational device is inserted into the patient.
- *Valve Implant (VI) Population:* all AT patient who received and retained the SAPIEN XT valve upon leaving the procedure room

All patients documented as part of the roll-in patient strategy will not be included in analysis population and evaluated separately.

The primary and secondary endpoints will be reported based on the AT Population. AT patients that did not receive the SAPIEN XT valve will be censored at 30 days or at resolution of any AE.

Descriptive and summary statistical analysis will be performed on all endpoints. Patient listings for adverse events, deaths, and reinterventions will include all enrolled patients.

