4.2 Secondary Endpoints

Safety

- Cardiovascular mortality at 30 days
- Stroke at 30 days
- TIA at 30 days
- All-cause mortality & stroke at 30 days
- Vascular complications (major) at 30 days
- Bleeding complications (life threatening or disabling, and major) at 30 days
- Myocardial infarction at 30 days
- Acute kidney injury at 30 days (stages II and III)
- Coronary obstruction requiring intervention at 30 days
- Permanent pacemaker implantation at 30 days

Device Success

- Absence of procedural mortality AND
- Correct positioning of a single prosthetic heart valve into the proper anatomic location AND
- Intended performance of the prosthetic heart valve (no prosthesis-patient mismatch and mean aortic valve gradient <20mmHg or peak velocity <3m/s, AND no moderate or severe prosthetic valve regurgitation) at 30 Days

Efficacy

- New York Heart Association (NYHA) Classification at 30 days
- Hemodynamic valve performance evaluation by echocardiography for aortic valve stenosis and aortic valve regurgitation (paravalvular & central) at 30 Days as determined by Echo core lab

5. Patient Population

To ensure that a minimum of 50 patients are implanted with the SAPIEN XT THV and complete the 30 Day follow-up for Primary Endpoint, up to 60 patients will be enrolled and implanted with SAPIEN XT THV. Each site may not contribute more than 30 implanted patients to the study population. All patients will be followed for 5 years.

Enrolment will be closely monitored to ensure not more than 60 patients are implanted with SAPIEN XT THV.

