6.3.3.6 Follow-Up Visits

The determination of the study endpoints will require rigorous clinical follow-up and quality data collection. The Investigator or delegated study personnel will ensure the patient is scheduled for follow-up visits according to Table 6.

Table 5Follow-up Visit Windows.

| Follow-Up Visit | Visit Window (days following Procedure) |
|-----------------|---|
| 30 Day | 30 days, +14 days |
| 6 Month | 180 days +/-30 days |

| 1 Year | 365 days +/-60 days |
|--------|----------------------|
| 2 Year | 730 days +/-60 days |
| 3 Year | 1095 days +/-60 days |
| 4 Year | 1460 days +/-60 days |
| 5 Year | 1825 days +/-60 days |

The importance of attending the 30 Day follow-up visit should be discussed with the patient. Planned absences should be recorded to facilitate continued ability to contact a study patient during the course of the study. If a patient cannot be reached for a follow-up visit, the investigator will document on the follow-up data form, the efforts undertaken to contact the patient, referring physicians, including internists as well as cardiologists, family members, or other alternate contacts noted in the study patient's records. These efforts should include 3 attempts of telephone contacts at separate dates and times, and a registered letter. If a patient can no longer be located, the investigator must contact an intermediary (e.g. patient's private physician) without delay.

Patients for whom the study procedure was begun but do not receive and retain the study valve will be followed up until the 30-day assessment or resolution of any AE for safety purposes. Patients with an ongoing AE at the 30 Day visit should have AEs reassessed at 30 day window closure (day 44). These patients should then be exited from the study. In the event that the patient's implanted valve is explanted, the patient needs to be followed up until resolution of any AE for safety purposes. These patients should then be exited from the study.

6.3.3.6.1 30-Day Visit

All patients will undergo the following assessments within the 30-Day follow-up period +14 days):

- Pertinent physical examination [include blood pressure, weight and all major systems findings]
- Adverse events
- Current cardiac medications and all medications given for cardiovascular effect
- NYHA functional classification
- CSS Angina Classification
- Neurological assessments
 - o NIHSS
 - o MRS
- 6 Minute Walk Test (6MWT)
- Clinical Laboratory Test

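### The As Treated rule in Section 11.3 also governs 30-day valve hemodynamics, so echoes from patients without a SAPIEN XT valve may be summarised as its performance

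*Combined protocol and SAP*

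**What the plan says.** Section 11.3 defines two sets.

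- **AT** covers enrolled patients "for whom the SAPIEN XT valve implant procedure was begun, defined as the time in which the first Edwards' investigational device is inserted". A valve in place is not required.
- **VI** is the subset described as "all AT patient who received and retained the SAPIEN XT valve upon leaving the procedure room".

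It then fixes the reporting set without exception: "The primary and secondary endpoints will be reported based on the AT Population". For AT patients without the valve it adds one handling rule: "AT patients that did not receive the SAPIEN XT valve will be censored at 30 days or at resolution of any AE".

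Section 4.2 lists among the secondary endpoints, at 30 days and read by the core laboratory, "Hemodynamic valve performance evaluation by echocardiography for aortic valve stenosis and aortic valve regurgitation", the latter both paravalvular and central. Section 11.5 adds that regurgitation grades will also be shown as shift from baseline.

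On follow-up, Section 6.3.3.6 says that patients whose procedure was begun but who "do not receive and retain the study valve will be followed up until the 30-day assessment or resolution of any AE for safety purposes" then leave the study. For the 30-day visit the same section says: "All patients will undergo the following assessments within the 30-Day follow-up period". A comprehensive transthoracic echocardiogram is on that list. The discharge visit in Section 6.3.3.5 is likewise written for all study patients and also includes one.

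The condition that defines VI appears once more, in Section 6.3.2, where it decides who counts toward the 60 implanted patients. That is an enrolment count, not an analysis.

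**The concern.** Most endpoints in Section 4.2 ask what happened to patients in whom the procedure was attempted. AT is the right set for those, because dropping failed implants would flatter the device. The hemodynamic endpoint asks something else: how the implanted valve performs. A patient who left with a native stenotic valve or a different prosthesis has no SAPIEN XT gradient to report.

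Read literally, the rule in Section 11.3 puts such a patient's 30-day echo into the summary of SAPIEN XT performance. The distortion has no fixed direction:

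- an untreated stenotic valve would raise the mean gradient;
- paravalvular leak has no meaning around a native valve, so coding such a patient as having none would lower the reported leak rate;
- another prosthesis could move either figure up or down.

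If these patients have no 30-day echo, a smaller problem remains. The stated denominator (AT) would differ from the set actually summarised, with nothing to say how that is handled.

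**Working it through.** The plan states no figure on this point that could be reproduced. The sample size in Section 11.1 rests on regulatory agreement. The check is therefore a reading of the text followed by an illustration of size.

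**Step 1: can a non-recipient's echo reach the table?**

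| Question | Where | Answer |
|---|---|---|
| Is the patient in the reporting set? | 11.3 | Yes, once a device is inserted |
| Is the endpoint reported on that set? | 11.3 with 4.2 | Yes, as a secondary endpoint |
| Is an echo listed? | 6.3.3.5, 6.3.3.6.1 | Yes, at discharge and 30 days, for all patients |
| Is the patient still in follow-up? | 6.3.3.6 | To the 30-day assessment or until adverse events resolve |
| Does any sentence exclude the echo? | whole text | None found |

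The path is open but not certain. The censoring rule does not close it: censoring ends time at risk in a time-to-event analysis and does not say whether a measured gradient is averaged.

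**Step 2: how long can the effect last?** Patients without the valve leave the study after the 30-day assessment or once adverse events resolve. The effect is therefore confined to the discharge and 30-day echoes. Later echo summaries come from patients who left the procedure room with the valve.

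**Step 3: how large could it be?**

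Inputs:
- n, implanted patients: 50 to 60 (Section 5).
- k, AT patients without the valve who have an echo: not given; assumed 1, 3 or 6. Section 6.3.2 counts only implanted patients toward the 60, so AT can be as large as n + k.
- Mean gradients, two assumed pairs. The first is 40 mmHg without and 20 mmHg with the valve, borrowing the inclusion threshold in Section 5.1 and the device-success threshold in Section 4.2 purely as illustrative values. The second is 45 and 10 mmHg, which are assumptions only.

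Formulas:
- share of AT = k / (n + k)
- shift in mean gradient = share × (mean without valve − mean with valve)

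| n | k | Share of AT | Shift, 40 vs 20 mmHg | Shift, 45 vs 10 mmHg |
|---|---|---|---|---|
| 60 | 1 | 1/61 = 1.6% | 0.33 | 0.57 |
| 60 | 3 | 3/63 = 4.8% | 0.95 | 1.67 |
| 60 | 6 | 6/66 = 9.1% | 1.82 | 3.18 |
| 50 | 1 | 1/51 = 2.0% | 0.39 | 0.69 |
| 50 | 3 | 3/53 = 5.7% | 1.13 | 1.98 |
| 50 | 6 | 6/56 = 10.7% | 2.14 | 3.75 |

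For example, with n = 60, k = 6 and means of 45 and 10: 6/66 × 35 = 3.18 mmHg.

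The same share governs paravalvular leak. If the rate among implanted patients is r and all k others are coded as having none, the AT rate is r × n/(n + k). That is a relative fall of k/(n + k), or 1.6% to 9.1% with 60 implanted.

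With k = 0, AT and VI give identical results. On VI the share is 0% whatever k is.

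**The case against.** The strongest reply is that nothing in the protocol says these echoes will be averaged in. Patients without the valve are followed for safety, not valve performance, and their follow-up may end when adverse events resolve, possibly before any 30-day echo. The synopsis describes the visit schedule for patients implanted with the valve, which points away from a full 30-day work-up for the others. A sensible analyst might leave them out of a valve-performance table unprompted. This stands. A reader might infer from the AT rule that non-recipients' echoes certainly enter the performance figures, but the documents support only that they may.

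A second reply is that Section 11.5 defers further detail to a Statistical Analysis Plan, and no separate plan text is in the document available here. VI may be used there. This also stands as a limit: a reader might conclude that VI is never used, but that can be said only of the available text. The deferral does not settle the matter, because a later plan that put hemodynamics on VI would conflict with Section 11.3 unless that section were amended.

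A third reply is that the consequence is modest. The endpoint is descriptive, and no test, performance goal or success threshold is attached to the mean gradient. That is correct, and it limits the weight of the point. The endpoint is nevertheless a named secondary result in a study meant to support Chinese regulatory approval.

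**Conclusion.** The point holds for one endpoint. Section 11.3 applies AT to all secondary endpoints, and for 30-day echocardiographic valve performance this permits results from a native or non-study valve to be reported as SAPIEN XT performance. The available text gives VI no analysis.

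It should not be read as a case against AT for the secondary endpoints in general. AT remains right for mortality, the other safety endpoints and device success. A patient who leaves without the valve already fails the positioning component of device success, so no extra rule is needed there.

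The size rests on assumptions. With 60 implanted and 1 to 6 non-recipients with an echo, they make up 1.6% to 9.1% of AT, and the mean gradient shifts by about 0.3 to 3.2 mmHg under the two assumed pairs of means. The number of such patients is not given, and with none the effect is zero. This is a change worth making because the mismatch is plain and the remedy is nearly free, not because a large bias has been shown.

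**What to change.** Amend Section 11.3 so that the hemodynamic and regurgitation summaries, and the shift tables built from them, are reported on the VI Population. State that echoes from other AT patients are listed separately and not pooled. Keep AT for mortality, the other safety endpoints and device success, and carry the same wording into the Statistical Analysis Plan.

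VI is fixed on leaving the procedure room, so the amendment could also say how an echo is handled if the valve is explanted before day 30.

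The cost is a sentence or two of text. It needs no new data, visits or patients, and is best settled before results are seen.

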11.4 Missing Data

All possible steps will be taken to minimize missing data in the study, including monitoring of data forms for completeness and efforts to track and maintain contact with study subjects during the follow-up period.

11.5 Endpoint Analysis

Patient data listings and tabular and graphical presentations of results will be provided. All clinically relevant baseline and follow-up variables will be tabulated. Descriptive statistics will be used for continuous variables (e.g., mean, standard deviation, sample size, minimum, and maximum) and frequency tables or proportions for discrete variables.

Kaplan Meier estimates will be performed at the pre-specified follow-up times to project the estimates for time-related safety endpoints. The Kaplan-Meier analysis will be used to compute the 30-day mortality rate, the primary endpoint; the standard error and confidence limits will be computed using Greenwood's algorithm.

Echocardiographic data will be analyzed by an Echo core laboratory with respect to the degree of total aortic valve regurgitation (TVR) and paravalvular aortic valve regurgitation (PAR) according to the VARC-2 definitions [46].

These data and other categorical data (e.g., NYHA class) will also be presented as shift from baseline for each of the pre-specified follow-up periods.

More specific information regarding the statistical analysis will be presented in the Statistical Analysis Plan (SAP).

12. Study Administration

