6.3.4 Missed Visits

Every patient should be encouraged to remain in the study until they have completed the protocol-required follow-up period. If the patient discontinues prematurely from the study, the reason for discontinuation must be documented on the appropriate case report form (CRF). Possible reasons for premature discontinuation may include, but are not limited to the following:

- Withdrawal of consent: Patient decides to withdraw from the study. If a subject withdraws from the clinical investigation, the reason(s) should be recorded. If such withdrawal is due to problems related to the investigational device safety or performance, the investigator shall ask for the subject's permission to follow his/her status/condition outside the investigation.
- Lost to follow-up: All patients should be encouraged to return to the clinic for evaluation during follow-up (excluding 6 Month telephone visit). If a patient is unable to return to the clinic, 3 separate telephone calls should be made to attempt to bring the patient back into the clinic or obtain safety information. All attempts should be documented in the source documents. If the patient does not respond to the 3 telephone calls then the Investigator should send a certified letter to the subject.

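### Section 11.5 names only Kaplan-Meier for safety rates at follow-up times that probably run to 5 years; if deaths are censored, descriptive long-term rates of non-fatal events and cardiovascular death would be overstated (low priority)

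*Combined protocol and SAP*

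**What the plan says.** Section 11.5 (Endpoint Analysis) has two sentences on Kaplan-Meier. The general one is: "Kaplan Meier estimates will be performed at the pre-specified follow-up times to project the estimates for time-related safety endpoints". The next applies the method to 30-day mortality, the primary endpoint, with Greenwood standard errors and limits. The same section plans "frequency tables or proportions for discrete variables" and leaves further detail to the SAP. No separate SAP text is in the combined document.

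On follow-up, section 5 says "All patients will be followed for 5 years", and the last visit window in section 6.3.3.6 is "1825 days +/-60 days". Section 8.3 has adverse events reported until participation ends.

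Two passages point the other way. Section 4 lists every primary and secondary endpoint at 30 days. Section 11.2 ties endpoint analysis to the 30-day visit and describes the later visits only as long-term data collection.

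The one written censoring rule, in section 11.3, is "AT patients that did not receive the SAPIEN XT valve will be censored at 30 days or at resolution of any AE". Nothing says how a death is handled when the event being estimated is non-fatal, or is death from one cause only.

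**The concern.** When a death is treated as censoring, one minus Kaplan-Meier (1-KM) estimates the risk of, say, stroke as if patients who have died could still have one. It does not estimate the share of patients who actually have the event; the cumulative incidence does. For cardiovascular mortality the same problem arises with non-cardiovascular deaths.

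The gap grows with mortality, and this is a high-risk population. Section 2.2.2 cites 44.2% mortality at 3 years in the transcatheter arm of an earlier randomised trial of an earlier valve in the same family.

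At stake is the accuracy of the long-term safety rates. One report could also show a Kaplan-Meier figure and a crude proportion for the same event that disagree, with no rule on which is the reported rate.

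**Working it through.** The plan gives no long-term rate to reproduce, and no 5-year mortality, so both are assumed and shown as ranges.

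**Inputs from section 2.2.2 (earlier trial, transcatheter arm).** Mortality 3.4% at 30 days and 44.2% at 3 years; peri-procedural stroke 3.8%.

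**Assumptions.** 5-year mortality M of 20% or 50%; the later event rates below; the cardiovascular share of deaths.

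**Formulas.** With event hazard h and death hazard l, constant over a period of length t:
- 1-KM = 1 − exp(−ht)
- cumulative incidence (CIF) = h/(h+l) × (1 − exp(−(h+l)t))

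Later periods are multiplied by the probability of being alive and event-free at their start.

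**Constant rate, h = 0.03 per year.** l = −ln(1−M)/5 = 0.0446 (M = 20%) or 0.1386 (M = 50%). 1-KM = 1 − exp(−0.15) = 13.9%.
- M = 20%: CIF = 0.03/0.0746 × (1 − exp(−0.373)) = 12.5%; ratio 1.11.
- M = 50%: CIF = 0.03/0.1686 × (1 − exp(−0.843)) = 10.1%; ratio 1.37.

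**Purely peri-procedural.** 3.8% net event risk and 3.4% mortality by day 30, no later events. CIF = 3.74%; ratio 3.8/3.74 = 1.02, whatever the later mortality.

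**Mixed.** The same early part, then a further 5% net risk spread evenly to 5 years. 1-KM = 1 − 0.962 × 0.95 = 8.6%. The event-free survival at day 30 is 0.966 × 0.962 = 0.929. The later hazards are h = 0.0104 and l = 0.0383 (M = 20%) or 0.1339 (M = 50%).
- M = 20%: CIF = 3.74% + 4.24% = 7.97%; ratio 1.08, excess 0.6 points.
- M = 50%: CIF = 3.74% + 3.41% = 7.15%; ratio 1.20, excess 1.5 points.

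**Late onset.** No events to year 2, then 0.05 per year; 1-KM is again 13.9%. CIF = 11.9% (M = 20%) or 8.7% (M = 50%); ratios 1.17 and 1.60.

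**Cardiovascular death, share s of all deaths.** 1-KM = 1 − (1−M)^s; CIF = sM.

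| M | s = 50% | s = 90% |
|---|---|---|
| 20% | 10.56% vs 10% (1.06) | 18.19% vs 18% (1.01) |
| 50% | 29.3% vs 25% (1.17) | 46.4% vs 45% (1.03) |

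Section 10 counts deaths of unknown cause as cardiovascular, which favours the smaller figures.

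**Cross-check at 3 years without extrapolating mortality.** l = −ln(1 − 0.442)/3 = 0.1945. At 0.03 per year, 8.6% against 6.5%; ratio 1.31.

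**At 30 days.** With mortality of 3.4% to 6.5% (the two arms of that trial), the relative excess is 1.7% to 3.4%.

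**Against sampling error.** In simulated studies of 60 patients at the constant rate, the 5-year bias of 1.4 points (M = 20%) or 3.8 points (M = 50%) compares with a Kaplan-Meier standard deviation of 4.8 or 5.6 points.

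**The case against.** The strongest reply is that the affected output may not be planned. Every listed safety endpoint is at 30 days and section 11.2 places endpoint analysis there, so the Kaplan-Meier sentence could be read as confined to 30 days. That reading is possible. The plural follow-up times, and the separate sentence for 30-day mortality, make the longer reading more likely but not certain.

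Three further points stand. Censoring at death is not written. The SAP may already settle the matter. Proportions are also planned, and with complete follow-up they equal the cumulative incidence. They are not a full safeguard: section 6.3.4 provides for loss and withdrawal ("Withdrawal of consent: Patient decides to withdraw from the study"). With an assumed 20% random loss by 5 years, the simulated crude proportion is 9.3% against a cumulative incidence of 10.3% at 50% mortality.

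A reader might infer that long-term harms in general will be overstated by 11% to 37%. The documents do not support that. Those figures assume a constant event rate, which the documents do not give. The one stroke figure used here, 3.8%, is peri-procedural, and several listed events are mainly procedural. Nor do those figures apply to cardiovascular mortality, where only non-cardiovascular deaths compete.

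**Conclusion.** The point holds conditionally and at low priority. If deaths are censored and 1-KM is the reported rate after 30 days, non-fatal event rates at 5 years would be overstated by about 2% (peri-procedural), 8% to 20% (mixed) or 11% to 37% (constant rate), for assumed mortality of 20% to 50%. Late events or higher mortality would widen this. For cardiovascular death the overstatement is about 1% to 6% at 20% mortality and 3% to 17% at 50%, for cardiovascular shares of 90% down to 50% of deaths.

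It would be wrong to conclude that the plan has chosen an invalid analysis or that its main result is at risk. The text is silent on competing death rather than explicit about censoring it. The 30-day endpoints, all-cause mortality and death-or-stroke are essentially unaffected, and no test or decision rule uses the long-term rates. The bias overstates harm rather than flattering the device, and lies within sampling error at 60 patients. It is nonetheless systematic, and Greenwood limits do not reflect it.

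**What to change.** Keep Kaplan-Meier with Greenwood limits for all-cause mortality, including the primary endpoint, and for all-cause mortality or stroke. For any other safety rate reported after 30 days, state in section 11.5 or the SAP that:
- death is a competing event (for cardiovascular mortality, non-cardiovascular death);
- the Aalen-Johansen cumulative incidence, with its matching variance, is the reported long-term rate;
- 1-KM appears in a supplementary table for comparison with earlier device studies.

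If the SAP already says this, section 11.5 need only refer to it.

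The cost is a few sentences and a standard procedure on data already collected. The downside is slightly more analysis work and less direct comparability with older reports, which the supplementary table largely addresses.

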2.2.1 Disease Process

The pathophysiology of AS includes an increase in afterload, progressive hypertrophy of the left ventricle, and a decrease in systemic and coronary blood flow as consequences of valve obstruction. Typically, patients with AS are free from cardiovascular symptoms (e.g. angina, syncope and/or heart failure) until late in the course of the disease. However, once symptoms manifest, the prognosis is poor, especially when associated with congestive heart failure. Death in general, including sudden death, occurs primarily in symptomatic patients. Survival analyses have demonstrated that the interval from onset of symptoms to time of death is approximately two years in patients with heart failure, three years in those with syncope, and five years in those with angina [2]. Among symptomatic patients with moderate-to-severe AS treated medically, mortality rates after the onset of symptoms were approximately 25% at 1 year and 50% at 2 years and more than 50% of deaths were sudden [3].

Grading the severity of AS is based on a variety of hemodynamic and natural history data. According to the ACC/AHA guideline authors, AS is best described as a continuum. In patients with moderate-to-severe AS, valve area may decline up to 0.3 cm² per year and the systolic pressure gradient across the valve can increase by as much as 15-19 mmHg per year, with a higher rate of progression observed in elderly patients with coronary artery disease (CAD) and chronic renal insufficiency [4]. Relief of aortic valve obstruction typically results in an improvement of symptoms, hemodynamic parameters, and global left ventricle systolic function, as well as reversal of left ventricular hypertrophy [4,5].

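### Study exit after a failed implant or an explant can make censoring informative in the post-30-day Kaplan-Meier curves, whose population is not named

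*Combined protocol and SAP*

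**What the plan says.** - **Estimator.** Section 11.5: "Kaplan Meier estimates will be performed at the pre-specified follow-up times to project the estimates for time-related safety endpoints". Section 11.2 lists visits at 6 months and at 1, 2, 3, 4 and 5 years.
- **Failed implants, analysis.** Section 11.3: "AT patients that did not receive the SAPIEN XT valve will be censored at 30 days or at resolution of any AE".
- **Failed implants, follow-up.** Under Section 6.3.3.6, patients who "do not receive and retain the study valve will be followed up until the 30-day assessment or resolution of any AE" then leave the study, with a recheck at day 44 if an event is still open.
- **Explants.** The same section says that after an explant "the patient needs to be followed up until resolution of any AE for safety purposes. These patients should then be exited from the study". This can happen at any time during follow-up.
- **Length of follow-up.** Section 5: "All patients will be followed for 5 years". The Study Duration row of the synopsis says the same of subjects implanted with the valve.
- **Population.** Section 11.3 assigns AT to the primary and secondary endpoints. In Sections 4.1 and 4.2 these are tied to 30 days or to the procedure. No population is named for the later curves.
- **Missing data.** Section 11.4 covers prevention only. It gives no vital-status check after exit and no sensitivity analysis.

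**The concern.** Kaplan-Meier assumes that a censored patient has the same future risk as patients still under observation. Here the stated rules remove patients because the device failed. Deaths after exit are never collected, and the curve gives these patients the risk of patients whose valve is in place. If they go on without a working valve, the protocol's own background figure for medically treated symptomatic stenosis applies: "mortality rates after the onset of symptoms were approximately 25% at 1 year and 50% at 2 years". That is worse than the TAVI mortality cited in Section 2.2.2.

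At stake is the meaning of the 6-month to 5-year mortality estimates. Any bias grows with the number of device failures and is not reflected in Greenwood limits. A later SAP can change the estimator but cannot recover data that Section 6.3.3.6 stops collecting.

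**Working it through.** The plan gives no figure to reproduce: no exit counts, no expected long-term mortality, and a sample size set by regulatory agreement.

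**Inputs from the documents**
- TAVI mortality 3.4% at 30 days and 44.2% at 3 years; surgical mortality 44.8% at 3 years (Section 2.2.2).
- Medically treated mortality about 50% at 2 years (Section 2.2.1).
- Up to 60 retained valves (Sections 5 and 6.3.2).

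**Assumptions.** The number of exits, the risk after exit, and constant hazards.

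**Step 1: hazards**
- After day 30 with the valve retained: h = −ln(0.558/0.966)/(3 − 30/365) = 0.188 per year.
- Medical therapy: ln 2/2 = 0.347 per year. The hazard ratio (HR) is 0.347/0.188 = 1.84.
- Surgical figure, with constant hazards from day 0: ln(0.552)/ln(0.558) = 1.02.

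**Step 2: exits at day 30, closed form.** With k exits beyond 60 retained valves, f = k/(60 + k) and u = t − 30/365:

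Kaplan-Meier mortality minus true mortality = −0.966 × f × [exp(−h·u) − exp(−HR·h·u)]

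Example with k = 3, HR 1.84, 5 years: −0.966 × (3/63) × (0.397 − 0.182) = −0.0099, or −0.99 points.

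| Exits | HR | 1 year | 3 years | 5 years |
|---|---|---|---|---|
| 1 | 1.84 | −0.18 | −0.34 | −0.34 |
| 3 | 0.5 | +0.35 | +0.84 | +1.07 |
| 3 | 1.84 | −0.52 | −0.98 | −0.99 |
| 3 | 3 | −1.13 | −1.77 | −1.54 |
| 6 | 0.5 | +0.67 | +1.60 | +2.05 |
| 6 | 1.84 | −1.00 | −1.88 | −1.89 |
| 6 | 3 | −2.16 | −3.38 | −2.93 |

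At HR 1 the difference is zero at every time.

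**Step 3: explants added, by simulation.** There are 60 patients in all. The retained-valve hazard is −ln(0.558)/3 = 0.194 per year, and the hazard after failure or explant is 0.347. Failed implants are censored at day 30. Explant times are uniform over 5 years, occur only in survivors, and are censored one month later.
- 3 failed implants and 3 explants: Kaplan-Meier is 1.0, 1.3 and 1.5 points low at 2, 3 and 5 years.
- 5 and 3: about 1.6, 2 and 2.2 points low (repeat runs differ by up to 0.2).
- Explants only (0 and 3): about 0.2, 0.3 and 0.5 points low.
- 3 and 3 with the surgical mortality after exit: under 0.1 point at every time.

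Of 3 patients assigned an explant, some die first. The expected number explanted is 3 × (1 − exp(−5 × 0.194))/(5 × 0.194) = 1.9.

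**Step 4: precision.** With no other censoring, the standard error is √(0.187 × 0.813/60) = 5.0 points at 1 year and √(0.617 × 0.383/60) = 6.3 points at 5 years. In the simulation it is about 5 to 7 points.

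**Step 5: bounds without a hazard assumption after exit.** With 3 exits at day 30, all alive or all dead afterwards, true mortality is 18.0% to 22.6% at 1 year (Kaplan-Meier 18.7%) and 58.9% to 63.5% at 5 years (Kaplan-Meier 61.7%).

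**The case against.** The strongest reply is that the bias is neither documented nor large. Candidates must be operable (Section 5.1), and Section 6.3.6 expects enrolled patients not treated with the valve either to be screened for other treatment or to continue existing care. If exits follow the surgical mortality in Section 2.2.2, the bias vanishes. The exit counts are invented, every modelled bias is below one standard error, and the study is descriptive with no hypothesis or margin. Deaths before exit, including procedural deaths, still count. Section 11.5 defers detail to a SAP. All of this stands, and it limits the size and direction of the claim. It does not remove the exit rule.

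Four stronger readings go beyond the documents:
- **Long-term AT mortality is biased low.** A reader might infer this as fact. No long-term AT analysis is named. If the Valve Implant (VI) set were used, failed implants would drop out and only explants would matter. The direction depends on what happens after exit.
- **Explants are expressly censored.** Section 11.3 speaks only of patients who did not receive the valve. Censoring of explants is inferred from the exit rule, although ordinary Kaplan-Meier has little else to do with a patient whose later status is unknown.
- **The 5-year statement contradicts both exits.** In context it refers to patients enrolled and implanted, so the clear conflict is with the explant exit.
- **The worst device outcomes disappear.** AT keeps failed implants for the 30-day endpoints, and Section 11.3 lists deaths and reinterventions for all enrolled patients. Only what follows exit is lost.

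**Conclusion.** The point holds in limited form. The written rules tie loss from the risk set to device failure, expressly for failed implants and by inference for explants. The plan has no vital-status check after exit, no sensitivity analysis and no named population for the post-30-day curves.

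Mortality after day 30 may therefore be biased, probably low if exits remain without a working valve. Under the medical-therapy hazard with 3 failed implants and 3 explants among 60, the shortfall is about 1.0 to 1.5 points between 2 and 5 years. The largest modelled shortfall is 3.4 points (6 exits, HR 3, 3 years). The bias is near zero at the cited surgical mortality and reverses if exits do better than those who stay. It stays below one standard error throughout. Counts and hazards after exit are assumptions.

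This is a cheap improvement worth making before patients exit. It does not show that the planned results would mislead.

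**What to change.** 1. **Section 6.3.3.6.** Separate the end of device follow-up from study exit. With consent, collect vital status, and stroke where possible, by telephone at the scheduled visit times to 5 years. Do this for explanted patients and for AT patients without a valve. Reconcile this section with Section 5 and the synopsis.
2. **Sections 11.3 and 11.5.** Name the population for the post-30-day curves. State that explant, and implant failure if AT is used, is not a censoring event for all-cause mortality.
3. **Where status after exit is unavailable.** Report the number of such exits and best-case and worst-case bounds, and describe the curve as censored at explant or failed implant. Do not label it as the VI population with the valve in place: VI is fixed on leaving the procedure room and still contains patients explanted later.

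The cost is wording plus a few telephone contacts for a handful of patients. Section 6.3.3.6.2 already allows the 6-month visit by telephone. Reported long-term mortality may become slightly less favourable.
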